7. STUDY OUTCOMES

7.1. Primary outcome

The primary outcome will be the iGFR at the end of the 2-month wash-out period following the 3-year treatment period, measured by the plasma clearance of non-radioactive iohexol (iGFR) and adjusted for the iGFR at baseline. The rationale of measuring the primary outcome at the end of the wash-out period is to test allopurinol for permanent effects of on the natural history of kidney disease, independent from any transient, hemodynamic effect that the medication may have on GFR. Plasma iohexol clearance has been shown to provide accurate and reproducible GFR measurements.^{30,31} It is highly correlated with inulin clearance (the gold standard to measuring GFR)³² and is a safe, cost-effective method to test hundreds of patients enrolled in multicenter clinical trials.³³ The method consists of injecting a 5 mL bolus of Iohexol (Omnipaque, 300 mg iodine/mL) and drawing blood samples at baseline and 120, 150, 180, 210, and 240 minutes after the injection. Plasma concentrations of iohexol at different time points are measured by HPLC and used to calculate the plasma clearance of iohexol ($Cl = \text{Dose}/\text{AUC}$, where AUC is the area under the plasma concentration time curve), which is taken after appropriate body surface area corrections as a measure of GFR.^{30,31}

7.1.1. iGFR quality assurance

It is of the foremost importance that reliable iGFR measurements are obtained. To maximize accuracy and precision, the following procedure will be in place.

1. Personnel performing the iohexol clearance test will undergo a standardized training program administered under the Site Directors' supervision through in-person meetings or on-line modules. All clinical site staff will complete the online knowledge testing in order to perform the tests.
2. Participants will be instructed to discontinue non-steroidal anti-inflammatory drugs (NSAIDs) for at least 3 days and avoid large protein meals for one day prior to the test, since these

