8. STUDY PROCEDURES

8.1. Schedule of Events

The schedule of events that will take place in the proposed study is outlined in Figure 1. Visits will be frequent during the Run-In period and during the first 30 days after randomization in order to escalate the allopurinol dosage and closely monitor the occurrence of AEs. After that, participants will be seen every 3-4 months to monitor their UA levels, renal function, occurrence of AEs, and medication compliance and, if necessary, to perform interventions to improve compliance. Visit 1 will be considered as Time 0 for scheduling Visits 2-5, Visit 5 will be considered as Time 0 for scheduling Visit 6-16, Visit 16 as Time 0 for scheduling Visit 17. The study windows that define when study visits may occur are noted in Figure 1 and differ by type of visit. Visits 2, 3, and 6 will be carried out within 6 business days (before or after) from their scheduled dates; visits 11, 16, and 17 within 2 weeks before and 4 weeks after their scheduled dates; visit 4A (if necessary) within 1 week before and 3 weeks after its scheduled date, and all other visits within 2 weeks (before or after) from their schedule dates. Additional blood or urine samples may be required in between visits if clinically significant changes are observed in blood or urine measurements that need to be confirmed or otherwise monitored. iGFR measurements may be repeated for medical reasons or technical problems (see 7.1). Safety laboratory tests (CBC, serum creatinine, K^+ , ALT, and pregnancy tests in women) will be performed by local laboratories. Outcome variables (plasma iohexol, serum creatinine and cystatin C, urinary AER), HbA1c, and serum uric acid will be measured by the Central Laboratory at the University of Minnesota, directed by [name].

Figure 1. Schedule of Events

Year	1	1	1	1	1	1	1	1	1	1	2	2	2	3	3	3	3	3
Week	-12	-9	-7	-3	0	4	16	32	48	64	80	96	112	128	142	156	164	
Visit #	1	2	3	4	4a*	5	6	7	8	9	10	11	12	13	14	15	16	17
^Type of Visit: In-Person Visit Required (V); Phone Call (C); Other Visit (In-Person or Remote Visit, O)	O	V	O	V	V	C	O	O	O	O	O	V	O	O	O	O	V	V
EVENT	Screen	Run-in				RANDO 100 mg	Allopurinol or placebo										Wash-out	
		200-400 mg										EOS						
Informed Consent	x	x																
Demographics	x																	
Initial Medical Hx		x																
Interval Medical Hx and BP Control			x	x	(x)		x	x	x	x	x	x	x	x	x	x	x	x
Concomitant Meds	x	x	x	x	(x)		x	x	x	x	x	x	x	x	x	x	x	x

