8.7. End of Wash-out Period (Visit 17)

After the end of the treatment period, participants will enter an 8-week wash-out period at the end of which the following procedures will be completed:

- Obtain medical history.
- Review of concomitant medications and AEs.
- Measure height and weight and vital signs.
- Inspect for skin rash.
- Collect samples for clinical laboratory assessments as outlined in Figure 1 and for storage for later biomarker research.
- Perform pregnancy test in women of childbearing potential.
- Measure iGFR.

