13.2. Sources of research material

1. Specimens on patients obtained specifically for research purposes.
 - a. Renal function studies requiring multiple blood specimens drawn from an indwelling IV over 4-6 hours for measurement of glomerular filtration rate at yearly intervals.
 - b. Collection of urine for measurement of urinary albumin and creatinine at 3-4 month intervals.
 - c. Blood for measurement of serum UA, creatinine, and liver enzymes, and WBC at quarterly intervals.
2. Specimens or measures obtained quarterly as component of routine patient care
 - a. HbA1c
 - b. Blood pressure
 - c. Height and weight
3. Patient and family medical information.

All study participants will be assigned a unique study identifier and in no publications or public presentations will information be available which could identify individual study participants or their families.

13.3. Plans for recruitment of subjects and consent procedures.

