- j. Most of the participants will already be on RAS Blockers. For those who were not previously taking these medications, risks will be minimized by not prescribing RAS Blockers to participants who have contraindications to these drugs and by prescribing an ARB whenever ACE inhibitors are contraindicated. If adverse events develop that are deemed to be related to the use of RAS blockers, the dose of these drugs will be decreased, followed by their discontinuation if the problem persists (see 8.2. Run-in period), thus adhering to current standards of care. If receiving discontinuation of RAS blockade becomes necessary, BP will be managed by alternate drugs as described above.
- k. Blood pressure will be measured quarterly with the goal of maintaining BP ≤ 140 mmHg systolic and ≤ 90 mmHg diastolic. If elevated, a recheck will be performed within 2 weeks and if still elevated additional antihypertensive non-RAS blockers will be added in collaboration with the participants' physicians. Failure to achieve satisfactory BP control within 2 months would lead to a case review by the Drug Monitoring Committee.
- l. Participants with a decrease in both iGFR (meeting the R^2 criterion described in 7.1.2) and eGFR from one measurement to the following one corresponding to a GFR decline $> 20\%$ per year will be referred to a nephrologist to investigate the causes of such rapid loss of kidney function. If a decrease of such magnitude is observed for the iGFR but is less than a 20%

decline per year for the eGFR, the iGFR measurement will be repeated. If the >20% per year iGFR decrease is confirmed, the participant will be referred to a nephrologist for further evaluation. In this case, the first iGFR value will be used for the analysis of the primary outcome. If the >20% per year iGFR decrease is not confirmed, the participant will not be referred to a nephrologist. The first iGFR test will be reviewed to verify whether medical conditions that should have prompted a test postponement, such as dehydration or recent use of NSAID (see 7.1.1.3), were present. In that case, the repeated iGFR value will be used for the primary outcome analysis. Otherwise, the first iGFR value will be used.

- m. Data monitoring will be performed on a regular basis. Data entry computers will be programmed to flag any parameters outside clinically acceptable ranges.

c. Protection of confidentiality

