6.3. Visit windows

To provide scheduling flexibility to study sites and participants, visits were required to occur within a protocol-defined window rather than on a specific date. The protocol-defined visit windows are summarized in the tables 6.3.1 and 6.3.2 below. For analytic purposes, the visit windows defined in the protocol will be expanded in order to eliminate gaps between them. This will ensure that all observations, including those that may have occurred outside a protocol-specified time window, will be associated with the most appropriate visit and therefore properly included in the analysis. If multiple observations occur within a window, the one closest to the visit target date will be utilized. If two observations are equi-distant from the target date, the first one will be utilized.

As iGFR is the primary and key secondary endpoint, the protocol allowed for repeats of the iGFR procedure in order to achieve qualified iGFR values. Also, the procedure required a longer visit, so it was more difficult to schedule. Thus, we allowed wider windows for iGFR visits (V11, V16 and V17) to ensure that all qualified iGFRs are analyzed. In addition to avoid over-writing iGFR visits with a non-iGFR (V6-V10, V12-V15) visit, and vice-versa the aforementioned procedure will be performed separately for non-iGFR (Table 6.3.1) and iGFR visits (Table 6.3.2).

Table 6.3.1. PERL windows for post-randomization non-IGFR visits.

Visit	Lower Boundary of Window (Week, Excluding First day)	Per protocol Target Date window in weeks	Upper Boundary of Window (Week, Including last day)	Time since randomization attributed to visit window (in weeks)
Visit Windows relative to Randomization Date				
Visit 6	0	4 [3-5]	10	5
Visit 7	10	16 [14-20]	24	17
Visit 8	24	32 [30-34]	40	32
Visit 9	40	48 [46-50]	56	48
Visit 10	56	64 [62-66]	72	64
Visit 12	88	96 [94-98]	104	96
Visit 13	104	112 [110 -114]	120	112
Visit 14	120	128 [126 -130]	135	128
Visit 15	135	142 [140 -146]	150	142

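### The >20% per year GFR trigger has no minimum interval, so at Visit 17 it acts on a fall of about 3%; Protocol 13.5 and SAP 6.3 can also name different Visit 17 values for the primary analysis

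*Protocol*

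**What the plan says.** **The trigger.** Protocol 13.5.b.7.l compares consecutive GFR values and converts the change to a yearly rate. A participant is referred to a nephrologist when iGFR and "eGFR from one measurement to the following one corresponding to a GFR decline" both exceed 20% per year. If only iGFR exceeds it, the iohexol test is repeated, and referral follows if the repeat confirms the fall. No minimum interval, minimum absolute fall or exception for any visit is stated.

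**The timing.** Under Protocol 8.7, "participants will enter an 8-week wash-out period at the end of which" Visit 17 takes place. Protocol 8.1 schedules "visits 11, 16, and 17 within 2 weeks before and 4 weeks after their scheduled dates", so V17 may fall 6 to 12 weeks after V16.

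**The value analysed.** Protocol 13.5.b.7.l also decides which test enters the primary analysis. If the fall is confirmed, the first value is used. If it is not confirmed and the first test was done under a condition that should have postponed it (dehydration or recent NSAID use, for example), the repeat is used. "Otherwise, the first iGFR value will be used" in the remaining case. SAP 6.3 has a different general rule: "If multiple observations occur within a window, the one closest to the visit target date will be utilized", with ties going to the first. For V17 the target is week 8 after V16, and the analysis window runs to week 20. SAP 6.3 notes that "the protocol allowed for repeats of the iGFR procedure in order to achieve qualified iGFR values", but does not mention 13.5.b.7.l.

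**The concern.** An annualised threshold needs an interval long enough for real change to outweigh test error. Protocol 13.2 describes samples "drawn from an indwelling IV over 4-6 hours for measurement of glomerular filtration rate at yearly intervals", and a yearly rate suits that spacing. It does not suit 8 weeks, where the same rate is a fall of a few percent. Followed as written, the rule would send participants who have just completed their last scheduled visit for another iohexol test lasting several hours, or to a nephrologist, largely on noise.

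The second issue concerns the primary endpoint directly. A participant with two acceptable V17 tests should have one analysed value fixed in advance. Here two documents each give a rule, and the rules do not always agree.

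**Working it through.** **1. Size of the trigger.** The plan states no per-interval threshold, so there is no figure to reproduce. Visit weeks come from the schedule of events (V4 at week -3, V11 at 80, V16 at 156, V17 at 164). Linear: 20% x weeks/52. Compound: 1 - 0.8^(weeks/52).

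| Interval | Weeks | Linear | Compound |
|---|---|---|---|
| V4-V11 | 83 | 31.9% | 30.0% |
| V11-V16 | 76 | 29.2% | 27.8% |
| V16-V17, earliest | 6 | 2.3% | 2.5% |
| V16-V17, target | 8 | 3.1% | 3.4% |
| V16-V17, latest | 12 | 4.6% | 5.0% |

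At an iGFR of 70, the week-8 trigger is 70 x 0.0308 = 2.2 ml/min/1.73 m².

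**2. Against measurement error.** Protocol 7.1 says only that "Plasma iohexol clearance has been shown to provide accurate and reproducible GFR measurements"; no CV is given. The 95% range for the difference between two tests is 1.96 x √2 x CV. Setting this equal to 3.08% gives CV = 3.08/(1.96 x 1.414) = 1.11%. For any CV above 1.1%, the trigger lies inside test-retest noise.

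**3. How often it would fire (illustrative).** Assumed: iGFR CV 2% to 10%, and a true decline of 4.5% per year in everyone (3 ml/min per year from Protocol 11.10, at an assumed level of about 67). Any real shift on stopping the drug is ignored. Over 8 weeks the true fall is 4.5% x 8/52 = 0.69%. At a CV of 2% the chance of exceeding 3.08% is roughly the normal upper tail at (3.08 - 0.69)/(1.414 x 2) = 0.85, about 20%. Simulation with 1,000,000 participants per scenario gives:

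| Interval | Trip the iGFR trigger, CV 2% to 10% |
|---|---|
| V16-V17, 6 weeks | 26.1% to 44.9% |
| V16-V17, 8 weeks | 19.5% to 43.2% |
| V16-V17, 12 weeks | 9.7% to 39.9% |
| V11-V16 | 0.0% to 2.7% |
| V4-V11 | 0.0% to 1.6% |

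At week 8 with a CV of 1% the figure is 4.3%. With no true decline at all it is 13.4% to 41.1% for CVs of 2% to 10%, so most week-8 triggers come from error. With 530 randomised (SAP 1) and 15% dropout (Protocol 11.10), 530 x 0.85 = 450 would be tested; 19.5% to 43.2% of these is 88 to 194.

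The split between repeat and direct referral depends on eGFR error (CV assumed 5% to 7%) and its correlation with iGFR error. At week 8:

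- independent errors: repeat 12% to 27%, direct referral 7% to 17%;
- correlation 0.5: repeat 6% to 20%, direct referral 13% to 25%.

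**4. The two selection rules.** Let the first V17 test be at week f after V16 and the repeat d weeks later, both technically acceptable.

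- **(a) Protocol keeps the first test.** For f below 8, SAP 6.3 takes the repeat if d < 2 x (8 - f): under 4 weeks after a week-6 test, or under 2 weeks after a week-7 test. In whole weeks the conflicting first/repeat pairs are 6/7, 6/8, 6/9 and 7/8. For f of 8 or more this direction never arises.
- **(b) Protocol takes the repeat.** SAP 6.3 takes the first test whenever it is at least as close to week 8. That covers every first test at week 8 or later, and early first tests whose repeat comes late enough, such as 6/10.

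With first tests at weeks 6 to 12 and repeats up to week 20 there are 77 whole-week pairs: 4 conflict under (a) and the other 73 under (b). These count possible timings, not participants.

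**The case against.** **It is a safety screen with two gates.** A 3.1% iGFR fall alone leads only to a repeat; referral needs eGFR to cross the rate too, or the repeat to confirm. A reader might infer that a 3% iGFR fall sends people straight to a nephrologist. The text does not say that. Preferring sensitivity is a legitimate choice, but nothing suggests that a screen roughly ten times more sensitive at one visit was intended.

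**The burden rests on assumed inputs.** This stands. The CVs, the error correlation and the uniform decline are not in the documents. V16-V17 is also when the drug is withdrawn, and Protocol 7.1 allows for a transient haemodynamic effect, so some falls could be real and could differ by arm. The 88 to 194 should not be read as a forecast. The 1.1% CV bound does not depend on these inputs.

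**The Manual of Operations may cover it.** Protocol 14 places follow-up of flagged results there, and its content is not available. It may add operating detail, but the protocol rule still stands as written.

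**The documents can be read together.** SAP section 3 lists departures from the protocol and names no change to this rule; 3.4 concerns only time zero for the visit windows. So the specific protocol rule arguably survives the general one. That is a fair reading, but SAP 6.3 never says so, and its word for acceptable tests does not settle the matter because both can pass the R² criterion.

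**Both conflicts are limited.** Direction (a) needs central assay, quality control and a repeat visit completed within a few weeks of an early test. Direction (b) is partly covered by Protocol 7.1.3, which drops a test when a contraindication is confirmed and cannot be corrected. However, 13.5.b.7.l says only that the repeat is used, not that the first is dropped.

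**Conclusion.** The point holds and is worth correcting. At V17 the rule acts on a fall of about 3.1% (2.3% to 4.6% over the window), within test-retest error for any iGFR CV above 1.1%. For assumed CVs of 2% to 10%, roughly 10% to 45% of those tested would trip the iGFR trigger across weeks 6 to 12; these figures are illustrative.

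The documents can also select different V17 values for the primary endpoint, in both directions. A reader might infer that the primary estimate is materially biased. The documents do not support that: the conflict needs two acceptable tests at particular timings, its frequency cannot be estimated, and any bias is likely small. The defect is an avoidable retest and referral burden plus an analysed value not uniquely fixed in advance.

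**What to change.** **Protocol 13.5.b.7.l.** For V16-V17, replace the annual rate with an absolute fall from V16 clearly above iohexol measurement error, chosen by the investigators from their own repeatability data. For CVs of 2% to 10%, and under the same assumptions, a fall above 20% would flag 0% to 7%, above 15% 0% to 14%, and above 10% 0% to 24%; 15% to 20% looks reasonable. Exempting the interval altogether is not advised, because no fall at the last visit, however large, would then prompt referral under this rule.

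**SAP 6.3.** Add one sentence: for safety-triggered repeats, the value named in Protocol 13.5.b.7.l is analysed, and the other test does not enter the closest-to-target selection. This settles both directions.

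**Cost.** One protocol clarification and one SAP sentence, with fewer repeats and referrals. The downside is that true 8-week falls between about 3% and the new threshold would no longer trigger this rule.

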13.6. Incentives/remuneration

If allowed by local regulations, participants will be reimbursed for the time and effort associated with participating in this study. Reimbursement amounts will be decided locally. Payments will be made at each visit. Participants with financial hardships deriving, for example, from loss of income or child care costs, may be reimbursed for such costs on a case by case basis. Participants who do not complete the whole study will only be reimbursed for the visits they completed. Transportation costs (e.g., parking or public transportation) may be reimbursed according to local policies. Remote site participant costs associated with travel to a Main Site will be reimbursed according to Federal travel, hotel, and per diem rates (gsa.gov).

13.7. Institutional Review Board

The protocol and informed consent forms and subsequent modifications will be reviewed and approved by the Human Subject Committees at all the centers involved in the study for compliance with applicable standards/regulations.

14. DATA AND SAFETY MONITORING PLAN

The Data and Safety Monitoring Plan for this study includes the following elements:

1. A *Data Safety Monitoring Board (DSMB)*, including outside experts in the design and conduct of clinical trials and in diabetic nephropathy, will be established by NIH. The purpose of the DSMB is to assure independent review as to whether study patients are exposed to unreasonable risk because of study participation, and to monitor study progress and integrity. The DSMB will receive detailed data from the Data Coordinating Center as frequently as deemed appropriate by the board, including summary tabulations and narratives of adverse events, and will meet periodically with the Study Investigators and the Data Coordinating Center personnel. They will have full access to all data, and their recommendations and input will be given high priority and will be incorporated into the study protocol. To this end, the DSMB will meet separately, "*in camera*" (Closed Sessions), with the Co-Director of the Data Coordinating Center, [name], to review all adverse event data in relation to the randomized treatment groups in order to detect any increased frequency of significant adverse events which could be study drug related, and decide whether continuation of the trial is warranted.
2. *IRB monitoring* will be in place from:
 - ◆ Joslin Diabetes Center
 - ◆ University of Minnesota
 - ◆ University of Colorado
 - ◆ University of Michigan
 - ◆ Northwestern University
 - ◆ University of Toronto
 - ◆ Albert Einstein University
 - ◆ Washington University
 - ◆ Steno Diabetes Center
 - ◆ University of Calgary
 - ◆ University of Alberta
 - ◆ Emory University
 - ◆ University of Washington
 - ◆ University of Texas Southwestern
 - ◆ Providence Medical Research
 - ◆ BC Diabetes
3. *SAE reporting*.

All adverse events are reported to the DCC by completion of the Adverse Events Form. All SAEs as defined previously will require expedited event notification within 72 hours of occurrence or identification to the DCC. The DCC will promptly notify the study PIs, who may convene a Drug

Monitoring Committee (DMC) conference to acquire further information about the event and take appropriate actions concerning the study medication (see Section 15.1).

An independent physician not involved in the study will serve as the Medical Safety Officer, reviewing all SAEs promptly after being reported in the database by the clinical sites. Based on the clinical site report and any additional input from the DMC, the Medical Safety Officer will prepare a preliminary SAE narrative report (in cases where the SAE is not resolved) for each SAE which will be distributed to the PIs, NIDDK Program Director, DSMB Chair, clinical site director, and appropriate DCC staff. Once the SAE is resolved, a final SAE narrative report is generated by the Medical Safety Officer. This report will be sent to the clinical site PI to review for accuracy and completeness. Following review by the clinical site PI, the Medical Safety Officer will send the final SAE narrative report to the PIs, NIDDK Program Director, DSMB Chair, clinical site director, and appropriate DCC staff. All SAE narrative reports, both preliminary and final, will be reviewed by the DSMB during their regularly scheduled meetings or on an expedited basis as determined by the NIDDK Program Director, who will solicit the input of the Chair of the DSMB as needed. The FDA definitions and requirements for expedited reporting will be used to determine if any individual SAE warrants notification to the FDA and to the IRBs of all participating PERL clinical sites.

The clinical site at which the SAE occurred is responsible for expedited reporting of the SAE to their respective IRB. Each site is responsible to report all AE's to their IRB according to its AE reporting policy and procedures.

On behalf of the NIDDK, the Data Coordinating Center will submit an expedited safety report to the FDA for all serious unexpected suspected adverse reactions (SUSARs). That is, when the SAE is unexpected and may be related to the study drug based on evidence of causality. This report will include information on frequency of similar events along with a narrative of similar events to provide context for the individual report. Copies of the expedited safety report will be provided to the PIs, NIDDK, DSMB, and site investigators.

4. When collecting data on participants, adequate safety levels will be set for flagging test results. When these levels are reached, the Data Coordinating Center will notify the appropriate clinic that an abnormal result has been received. Detailed follow-up procedures will be set in the Manual of Operations that will be followed by the clinic when any abnormal results are received.
5. Monthly conference calls will be scheduled for the Steering Committee (SC) and the Trial Coordinators. Subject participation and compliance will be discussed in detail during these calls. A clinical psychology expert in the behavioral and compliance aspects of clinical trials, [name] from the University of Minnesota, will be included in the Trial Coordinator calls when discussing participant compliance issues.
6. A Drug Monitoring Committee (DMC) consisting of the PERL Center Directors and PIs, a research pharmacist, and the Project Manager will discuss any serious medication related problem that a participant has. Changes in study medication dose, medication discontinuation and medication re-institution will be included in these discussions.
7. Twice a year, the Study Group will meet face-to-face with the Data Coordinating Center personnel for a 1½ day meeting to discuss the study in detail and any problems that may have occurred. The Trial Coordinators will hold a separate ½ day meeting with the Data Coordinating Center prior to the SC meeting and any issues needing discussion will be presented at that time and carried from and to the main Study Group meeting for discussion and resolution.

